5.2.6. Recommended Dose Modifications

Every effort should be made to administer study treatment on the planned dose and schedule.

In the event of significant toxicity, dosing may be delayed and/or dose reduced as described below. In the event of multiple toxicities, dose modification should be based on the worst toxicity observed. Patients are to be instructed to notify Investigators at the first occurrence of any adverse symptom. In addition to dose modifications, investigators are encouraged to employ best supportive care according to local institutional clinical practices and according to the guidance for selected adverse events provided below.

If a PLD dose reduction is necessary, the PLD dose should be reduced initially to 30 mg/m², and then down to 20 mg/m² if a second dose reduction is required. Management of patients requiring more than 2 PLD dose reductions should be discussed with the Sponsor. Do not increase PLD dose after a prior dose reduction due to toxicity.

Table 4. Dose Modifications for PLD

Dose Level	PLD
Starting dose	40 mg/m ²
First dose reduction	30 mg/m ²
Second dose reduction	20 mg/m ²

For avelumab, no dose modifications are permitted in this study, but doses may be omitted based on persisting toxicity.

For patients on avelumab plus PLD combination treatment, PLD dose modifications as well as infusion omissions/ delays for PLD and/or avelumab may occur independently for the two drugs according to the guidance provided below for each individual drug and investigator’s medical judgment and will be reported in the CRF. If PLD is delayed by 1 week, avelumab should also be delayed by 1 week so that PLD and avelumab are administered together.

Some potential immune-related adverse events described with anti-PD-L1 drugs such as avelumab may overlap with PLD toxicities such as rash or diarrhea. For patients on avelumab or combination treatment with avelumab and PLD, any adverse event suspected to be immune-related should be managed according to the guidance for management of immune-related adverse events [Appendix 9: Management of Immune-related Adverse Events](#)). In case of a potential irAE, besides the management related to avelumab therapy, PLD doses may also be modified or interrupted based on the guidance provided for PLD toxicity management ([Section 5.2.8.2 PLD Infusion-related Reaction](#)), product labeling, and institutional guidelines according to investigator’s medical judgment.

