5.2.7.2.3. Avelumab: Immune-related Adverse Events

Because inhibition of PD-L1 stimulates the immune system, irAEs may occur. Treatment of irAEs is mainly dependent upon severity (NCI-CTCAE grade):

- Grades 1 to 2: treat symptomatically or with moderate dose steroids, more frequent monitoring.
- Grades 1 to 2 (persistent): manage similar to high grade AE (Grades 3 to 4).
- Grades 3 to 4: treat with high dose corticosteroids.

For patients receiving avelumab or avelumab-PLD combination, any event suspected to be immune-related should be managed according to the guidance for management of immune-related adverse events in this [Section 5.2.7.2.3](#) and [Appendix 9](#). In case of a potential irAE, besides the management related to avelumab therapy, PLD doses may also be modified or interrupted based on the guidance provided for PLD toxicity management in [Section 5.2.8.2](#), product labeling, and institutional guidelines according to investigator's best medical judgement.

Effective with Amendment 2, [Table 6](#) below is no longer applicable and has been replaced with [Appendix 9](#). Please follow [Appendix 9](#) for all management of immune-related adverse events.

Table 6. No Longer Applicable: Avelumab: Management of Immune-related Adverse Events

Gastrointestinal irAEs		
Severity of Diarrhea/Colitis (NCI-CTCAE v4.03)	Management	Follow-up
Grade 1 Diarrhea: <4 stools/day over Baseline Colitis: asymptomatic	Continue avelumab therapy Symptomatic treatment (eg, loperamide)	Close monitoring for worsening symptoms Educate patient to report worsening immediately If worsens: Treat as Grade 2 or 3/4
Grade 2 Diarrhea: 4 to 6 stools per day over Baseline; IV fluids indicated <24 hours; not interfering with ADL Colitis: abdominal pain; blood in stool	Delay avelumab therapy Symptomatic treatment	If improves to Grade 1: Resume avelumab therapy If persists >5 to 7 days or recur: 0.5 to 1.0 mg/kg/day methylprednisolone or equivalent When symptoms improve to Grade 1, taper steroids over at least 1 month, consider prophylactic antibiotics for opportunistic infections, and resume avelumab therapy per protocol. If worsens or persists >3 to 5 days with oral steroids: Treat as Grade 3 to 4

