6.6.4. Other significant adverse events

The frequency (number and percentage) of patients with each of the following will be presented for irAEs, by treatment arm:

- irAEs leading to death, by Cluster and PT
- irAEs, by Cluster and PT

- irAEs, Grade ≥ 3 , by Cluster and PT
- irAEs leading to discontinuation of avelumab, by Cluster and PT
- irAEs leading to discontinuation of PLD, by Cluster and PT
- irAEs leading to discontinuation of any study drug, by Cluster and PT
- irAEs leading to discontinuation of all study drugs, by Cluster and PT
- Serious irAEs, by Cluster and PT

The listing of all irAEs will also be provided with the relevant information with a flag for irAEs with onset outside of the on-treatment period.

The frequency (number and percentage) of patients with each of the following will be presented for IRRs, by treatment arm:

- IRRs leading to death, by PT
- IRRs, by PT
- IRRs, Grade ≥ 3 , by PT
- IRRs leading to discontinuation of avelumab, by PT
- IRRs leading to discontinuation of PLD, by PT
- IRRs leading to discontinuation of any study drug, by PT
- IRRs leading to discontinuation of all study drugs, by PT
- Serious IRRs, by PT
- Time related to first onset of an IRR (infusion 1, infusion 2, infusion 3, infusion 4 or later). For IV study drugs administered in combination the infusion numbers are those associated with the regimen, rather than the individual study drugs.

The listing of all IRRs will also be provided with the relevant information with a flag for IRRs with onset outside of the on-treatment period.

In addition, the following analyses will be presented for Tier-1 (irAEs and IRRs as defined in Appendices 1 and 2) and Tier-2 events separately. P-values and CIs for risk difference will be calculated based on the unconditional exact method by Santner and Snell (1980). No additional analyses will be presented for Tier-3 AEs.

- Frequency (number and percentage) of patients with each of the following by treatment arm and PT or Clustered Term:
 - Tier-2 AEs
 - Tier-2 AEs Grade ≥ 3

- Point estimate for risk difference and 95% CI for risk difference (experimental arm vs comparator arm) for each of the following by PT or Clustered Term:
 - irAEs
 - irAEs Grade ≥ 3
 - IRRs
 - IRRs Grade ≥ 3
 - Tier-2 AEs
 - Tier-2 AEs Grade ≥ 3
- 2-sided p-value associated with risk difference (experimental arm vs comparator arm) for each of the following by PT or Clustered Term:
 - irAEs
 - irAEs Grade ≥ 3
 - IRRs
 - IRRs Grade ≥ 3

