9. APPENDICES

Appendix 1. Immune-Related Adverse Events

The MedDRA PTs and clusters for irAEs are defined in the Safety Review Plan (SRP) for avelumab.

Immune-related AEs (irAEs) will be programmatically identified as outlined in Table 16. This case definition is hierarchical, ie, each step is only checked for patients and events that have already met the prior step.

Table 16. Case Definition for irAEs

Step	Selection Criteria	Additional Notes
1	Event selected based on a list of pre-specified MedDRA PTs within clusters. These are included in the SRP as Tier1 events (Immune-mediated xxxx). If AE matches the list then it is in for the next step	
2	AE onset during 1 st study drug administration or anytime thereafter through 90 days after last dose of study treatment.	This is regardless of start of new anti-cancer drug therapy and regardless of TEAE classifications
3	Answer in the AE eCRF page to ‘Was another treatment given because of the occurrence of the event’ is ‘YES’	
4	AE treated with corticosteroids or other immunosuppressant therapy. For endocrinopathies only: AE required hormone replacement	Look in the conmed pages for AE identifiers that match the AEs from Step 3. For each of such AEs if A) OR B) below are met then the AE is in for the next step A) conmed ATC code is in (H02A, H02B, H02C, D07, A01AC, S01BA, S01BB, L04AA, L04AB, L04AC, L04AD, L04AX) and AE PT is in any of the irAE clusters. B) conmed ATC code is in (H03A, H03B) and AE PT is in one of the irAE clusters associated with “Immune-mediated endocrinopathies”

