
5
	
A) No clear etiology (other than immune mediated etiology)
 
B) Histopathology / biopsy consistent with immune-mediated event
 
Event is in if [Answer to 5B1 and 5B2 is YES (regardless of answer to 5A)] OR [Answer to 5B1 is YES AND answer to 5B2 is NO AND answer to 5A is NO] OR [Answer to 5B1 is NO AND answer to 5A is NO]
	
A) From the AE eCRF page Is the AE clearly related to an etiology other than immune-mediated etiology? Yes / No If answer is Yes, check all that apply:
 
 • Underlying malignancy / progressive disease. • Other medical conditions. • Prior or concomitant medications / procedures. • Other. Specify. 
B) From the AE eCRF page B1) Was there a pathology /histology evaluation performed to investigate the AE? Y/N B2) If answer to the above is Yes, does the pathology/histology evaluation confirms an immune mediated mechanism for the AE? Y/N B3) If pathology / histology evaluation performed to investigate the AE, provide summary of relevant findings of the pathology /histology report. (Free Text)

----------	---	--

The data set associated with irAEs may be refined based on medical review. The final data set including any changes based on medical review (eg, addition of cases that are not selected by the programmatic algorithm) will be the basis of the irAE analyses.

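### The irAE comparison with PLD probably under-counts irAEs in Arm C, because the case definition filters on steroid treatment and open-label attribution

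*Protocol*

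**What the plan says.** **Case definition.** SAP Appendix 1, Table 16 identifies irAEs in five steps, and "each step is only checked for patients and events that have already met the prior step".

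- Step 1: the preferred term is on a list held in the Safety Review Plan.
- Step 2: onset falls between the first dose and 90 days after the last dose.
- Step 3: another treatment was given because of the event.
- Step 4: "AE treated with corticosteroids or other immunosuppressant therapy", matched through the event's identifier on the medication pages. Hormone replacement also qualifies, for endocrinopathies only.
- Step 5: an etiology check. The investigator answers "Is the AE clearly related to an etiology other than immune-mediated etiology". Pathology that confirms an immune mechanism keeps the event whatever that answer is.

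The final irAE set may also be changed by medical review.

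**Management.** Protocol 5.2.6 says of the avelumab-containing arms: "For patients on avelumab or combination treatment with avelumab and PLD, any adverse event suspected to be immune-related should be managed according to the guidance". Section 5.2.7.2.3 repeats the restriction ("For patients receiving avelumab or avelumab-PLD combination, any event suspected to be immune-related should be managed according to the guidance") and includes "Grades 3 to 4: treat with high dose corticosteroids". The same 5.2.6 says some potential immune-related events "may overlap with PLD toxicities such as rash or diarrhea". For PLD, Table 11 covers other non-hematologic toxicity by delaying and reducing PLD, and names no steroid.

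**Comparison.** SAP 6.6.4 gives a risk difference with 95% CI, and a "2-sided p-value associated with risk difference (experimental arm vs comparator arm) for each of the following by PT or Clustered Term", for irAEs and for Grade 3 or higher irAEs.

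**The concern.** Steps 3 to 5 select on what happened after randomisation: whether the event was treated with a particular class of drug, and what an unblinded investigator blamed it on. Both can differ between arms for the same clinical event. The protocol tells sites to manage suspected immune-related events by the steroid guidance in Arms A and B. It gives no such instruction for Arm C, where PLD is an obvious alternative explanation for rash or diarrhea.

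Comparing with Arm C is useful because it subtracts the background, meaning the listed events that would have been counted without avelumab. If the filter passes more of that background in Arms A and B than in Arm C, too little is subtracted, and the remainder is reported as an effect of avelumab.

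The plan has no unfiltered comparison of these clusters to reveal this. TEAE tables by SOC and PT (SAP 6.6.1.1) carry no risk difference and stop at the end of the on-treatment period. Tier-2 risk differences exclude Tier-1 events by definition (SAP 3.5.1).

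**Working it through.** The documents state no irAE rate by arm and no power for this comparison, so there is no plan figure to reproduce.

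**1. What Step 5 does.** Going through its answer patterns:

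| Other clear cause? | Pathology | Result |
|---|---|---|
| No | not done | kept |
| No | done, not confirming | kept |
| No | done, confirming | kept |
| Yes | not done | dropped |
| Yes | done, not confirming | dropped |
| Yes | done, confirming | kept |

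An event blamed on another cause survives only with confirming pathology. Because the steps are hierarchical, pathology cannot rescue an event already lost at Step 3 or 4; only medical review can.

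**2. Size of the gap.** Let q be the background rate of events meeting Steps 1 and 2, taken as equal in both arms so that there is no true difference. Let c be the share of those events that passes Steps 3 to 5. Then:

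- counted rate = q × c
- spurious risk difference = q × (c in the avelumab arm − c in Arm C)

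Neither q nor c is in the documents. Both are assumptions:

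| q | c, avelumab arm | c, Arm C | Counted rates | Gap (points) |
|---|---|---|---|---|
| 15% | 20% | 10% | 3.0% vs 1.5% | 1.5 |
| 15% | 30% | 5% | 4.5% vs 0.75% | 3.75 |
| 25% | 20% | 10% | 5.0% vs 2.5% | 2.5 |
| 25% | 20% | 5% | 5.0% vs 1.25% | 3.75 |
| 25% | 30% | 10% | 7.5% vs 2.5% | 5.0 |
| 25% | 30% | 5% | 7.5% vs 1.25% | 6.25 |

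The range is about 1.5 to 6 points. A different assumed pair, 50% against 25% at q = 20%, gives 0.20 × 0.25 = 5.0 points. Equal capture gives zero. The range is not a bound: 0.30 × (0.50 − 0.10) = 12 points.

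**3. False-positive rate.** SAP 6.6.4 names the Santner and Snell unconditional exact method but does not say whether outcomes are ordered by the raw or a standardised difference. At about 183 per arm (550/3), the chance of p < 0.05 differs greatly between the two versions, so no flag rate is quoted.

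**4. Is the Steps 1 and 2 set neutral?** Protocol 8.2 collects adverse events to 90 days after the last dose in every arm, which matches Step 2. It is not perfectly neutral: non-serious reporting ends when new anticancer therapy starts, and the window lengthens with time on treatment.

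**The case against.** A reader might infer that the Arm C rate is low by construction, that identical events count in Arms A and B but not in C, and that the bias always favours a higher rate on avelumab. The documents do not support that.

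- Table 16 applies to all arms. Protocol 5.4.6 allows therapeutic and prophylactic corticosteroids under site practice with no arm restriction, so Arm C events can pass Step 4.
- Steroids are not automatic on avelumab. In Appendix 9, Grade 1 diarrhea and the first management of Grade 2 diarrhea are symptomatic, and Grade 1 to 2 rash may get antihistamines. Such events can fail Step 4 in any arm.
- Arm B also receives PLD, so the alternative cause is available there too.
- Confirming pathology and medical review can restore events.
- SAP 3.5.1 calls safety analyses exploratory, and 6.6.4 limits these p-values and CIs to unadjusted screening and estimation. No decision rule uses them.

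A further fair point is that the term list is in the Safety Review Plan, so it is unknown whether plain rash and diarrhea terms are on it.

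These points rule out the absolute wording and limit the consequence. They do not remove the problem. Bias needs only unequal capture, and permission to use steroids in Arm C is weaker than direction to use them in Arms A and B. The pathology route needs a biopsy and acts only at Step 5. Medical review has no stated blinding or arm-neutral rule. The SAP's caveat speaks to multiplicity and precision, not to ascertainment.

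**Conclusion.** The concern holds as likely differential ascertainment. irAEs are likely under-ascertained in Arm C, and the risk differences against PLD are likely biased upward. Against Arm B the attribution part is weaker, but the difference in directed treatment at Steps 3 and 4 remains.

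The size cannot be derived from the documents. The illustrative 1.5 to 6 points rests on assumed event rates, assumed capture shares and no true difference. The direction rests on the inference that directed management leads to more AE-linked steroid use than permission alone.

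The consequence is limited to how a screening-level safety comparison is read. It does not touch the OS or PFS tests.

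**What to change.** In SAP 6.6.4, keep the planned irAE comparison and add:

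1. For each experimental arm against Arm C, a risk difference with 95% CI on all events meeting Table 16 Steps 1 and 2, by cluster, for any grade and for Grade 3 or higher.
2. By-arm counts of events dropped at each of Steps 3, 4 and 5.
3. A statement that the Steps 1 to 5 comparison is conditional on treatment and attribution and should be read beside the Steps 1 and 2 result.

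The cost is a re-run of the existing algorithm on data already collected, with output after Step 2 and a count at each later step. Protocol Section 9 reports that the final analysis is complete, so if the SAP is closed the same table can be run as a labelled post hoc supplement.

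The downside is real. The Steps 1 and 2 set is less specific. Protocol 1.2.2.5 lists rash and diarrhea among PLD toxicities above 20%, while treatment-related rates in the avelumab ovarian cohort were 8.0% and 10.7% (Protocol Table 3). If those terms are on the list, the added comparison could favour avelumab alone over PLD and mask immune toxicity. It therefore supplements the irAE analysis and should not replace it.

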5.2.8. Guidelines for PLD Single Agent and Avelumab-PLD Combination Toxicity Management

Dose modification (dose delays and dose change) for PLD due to ADRs should be made in accordance with the guidance provided below, product labeling and institutional guidelines. Starting dose for PLD and dose reduction levels are described in [Table 4](#) Dose Modification for PLD.

5.2.8.1. PLD Single Agent and Avelumab-PLD Combination: Neutropenia and Thrombocytopenia

ANC must be $\geq 1.5 \times 10^9/L$ and the platelet count $\geq 75 \times 10^9/L$ prior to the beginning of the following course of treatment. For patients who do not achieve haematological recovery on scheduled day of PLD treatment, complete blood counts should be performed twice weekly until the above defined limits are achieved. If haematological recovery is achieved within 14 days after the scheduled day of PLD treatment, resume PLD at the previous dose. If haematological recovery is not achieved 14 days or more after the scheduled day of the course, the patient will discontinue treatment. Administration of G-CSF or EPO is permitted according to approved indications and scientific recommendations.

Table 7. PLD Single Agent and Avelumab-PLD Combination: Treatment Modification for Neutropenia and Thrombocytopenia

Neutropenia and Thrombocytopenia	PLD single agent	Avelumab-PLD combination*
Grade 1	No PLD dose reduction/delay	No PLD dose reduction/delay Continue avelumab as per schedule
Grade 2	Delay PLD until toxicity resolves to ANC $\geq 1.5 \times 10^9/L$, platelets $\geq 75 \times 10^9/L$; then resume PLD at previous dose.**	Delay PLD until toxicity resolves to ANC $\geq 1.5 \times 10^9/L$, platelets $\geq 75 \times 10^9/L$; then resume PLD at previous dose.** Continue avelumab as per schedule.
Grade 3	Delay PLD until toxicity resolves to ANC $\geq 1.5 \times 10^9/L$, platelets $\geq 75 \times 10^9/L$; then resume PLD at previous dose.** If Grade 3 toxicity recurs, follow institutional guidelines.	Delay PLD until toxicity resolves to ANC $\geq 1.5 \times 10^9/L$, platelets $\geq 75 \times 10^9/L$; resume PLD at previous dose.** Continue avelumab as per schedule. If Grade 3 toxicity recurs, delay PLD and avelumab until toxicity resolves to ANC $\geq 1.5 \times 10^9/L$, platelets $\geq 75 \times 10^9/L$; then resume PLD at reduced dose** and avelumab at standard dose. If Grade 3 toxicity recurs with PLD at reduced dose, delay PLD until toxicity resolves to ANC $\geq 1.5 \times 10^9/L$, platelets $\geq 75 \times 10^9/L$; then resume PLD at the next reduced dose. ** For avelumab, 
 • If toxicity resolves to ANC $\geq 1.5 \times 10^9/L$, platelets $\geq 75 \times 10^9/L$ within ≤ 14 days, resume avelumab at the standard dose. • If toxicity resolves to ANC $\geq 1.5 \times 10^9/L$, platelets $\geq 75 \times 10^9/L$ in > 14 days, permanently discontinue avelumab.
Grade 4	Delay PLD until toxicity resolves to ANC $\geq 1.5 \times 10^9/L$, platelets $\geq 75 \times 10^9/L$; then resume PLD at reduced dose level or continue at previous dose with prophylactic granulocyte growth factor support.**	Delay PLD and avelumab until toxicity resolves to Grade ≤ 1 ; then resume PLD at reduced dose level** and avelumab at standard dose. If Grade 4 toxicity recurs with PLD at reduced dose, delay PLD until toxicity resolves to ANC $\geq 1.5 \times 10^9/L$, platelets $\geq 75 \times 10^9/L$; then resume PLD at the next reduced dose. ** For avelumab, 
 • If toxicity resolves to ANC $\geq 1.5 \times 10^9/L$, platelets $\geq 75 \times 10^9/L$ within ≤ 14 days, resume avelumab at the standard dose. • If toxicity resolves to ANC $\geq 1.5 \times 10^9/L$, platelets $\geq 75 \times 10^9/L$ in > 14 days, permanently discontinue avelumab.

* For patients on avelumab alone, refer to [Section 5.2.7.1](#).

**If haematological recovery is achieved within 14 days after the scheduled day of PLD treatment, resume PLD at the previous dose. If PLD is delayed by 1 week, avelumab should be delayed by 1 week so that PLD and avelumab are administered together. If haematological recovery is not achieved 14 days or more after the scheduled day of the course, the patient will permanently discontinue treatment.

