Grade 3: Blistering, ulceration, or swelling interfering with walking or normal daily activities; cannot wear regular clothing.	Delay PLD dosing up to 2 weeks or until resolved to Grade ≤ 1 , then resume PLD treatment at decreased dose level. Discontinue PLD if there is no resolution after 2 weeks.	Delay PLD dosing up to 2 weeks or until resolved to Grade ≤ 1 , then resume PLD treatment at decreased dose level. Discontinue PLD if there is no resolution after 2 weeks. Delay avelumab until resolved to Grade ≤ 1 ; then resume avelumab. If PLD treatment was permanently discontinued and Grade ≥ 3 HFS subsequently recurs, avelumab should also be permanently discontinued.
Grade 4: Diffuse or local process causing infectious complications, or a bed ridden state or hospitalization.	Delay PLD dosing up to 2 weeks or until resolved to Grade ≤ 1 , then resume PLD treatment at decreased dose level. Discontinue PLD if there is no resolution after 2 weeks.	Delay avelumab until resolved to Grade ≤ 1 ; then resume avelumab. If PLD treatment was permanently discontinued and Grade 4 HFS recur, avelumab should also be permanently discontinued.

* For PLD-avelumab combination, PLD dosing should be managed as per PLD guidance.

**If PLD is delayed by 1 week, avelumab should be delayed by 1 week so that PLD and avelumab are administered together.

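### After Grade 4 or recurrent Grade 3 cytopenia in Arm B, Table 7 and its own footnote give different PLD doses

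*Protocol*

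**What the plan says.** The avelumab-PLD column of Table 7 grades its instructions by severity and recurrence. Grade 2 and first Grade 3 events resume PLD at the previous dose. The other cases step down:

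- Recurrent Grade 3: "then resume PLD at reduced dose and avelumab at standard dose".
- Grade 3 or Grade 4 recurring on an already reduced dose: "then resume PLD at the next reduced dose".
- First Grade 4: "then resume PLD at reduced dose level and avelumab at standard dose".

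All of these carry the double-asterisk footnote. That footnote states: "If haematological recovery is achieved within 14 days after the scheduled day of PLD treatment, resume PLD at the previous dose". If recovery has not come by 14 days, treatment stops permanently. The body text of Section 5.2.8.1 repeats the previous-dose rule. It follows an instruction that defines who is meant: "For patients who do not achieve haematological recovery on scheduled day of PLD treatment, complete blood counts should be performed twice weekly".

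Section 5.2.8 introduces all of this by saying that PLD modifications "should be made in accordance with the guidance provided below, product labeling and institutional guidelines".

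**The concern.** The footnote is attached to the reduced-dose instructions themselves, so it qualifies them, yet it orders a different dose. A site that follows the cell and a site that follows the footnote can both claim compliance while re-dosing the same patient one PLD level apart, after a severe or repeated cytopenia.

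The text is still in force. Amendment 2 retired Table 6 but not Table 7, and the revised schedule in Appendix 7 still gives PLD in Arm B.

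There is also a reporting consequence. Section 8.4 treats a dose 5% or more above the calculated dose as an overdose, and SAP Section 6.5.2.2 lists incorrect dosing among reportable deviations. If the cell governs, a dose given under the footnote passes that threshold. If the footnote governs, it does not.

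**Working it through.** No sample size, power or alpha figure is involved. The check is a side-by-side reading, followed by simple arithmetic on the dose levels.

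*Step 1: count the conflicts.* These are the footnoted PLD resumption instructions in the avelumab-PLD column, for a patient whose counts recover within 14 days after the scheduled day:

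| Event | Cell | Footnote and body text | Agree? |
|---|---|---|---|
| Grade 2 | previous | previous | yes |
| First Grade 3 | previous | previous | yes |
| Recurrent Grade 3 | reduced | previous | no |
| Grade 3 on a reduced dose | next reduced | previous | no |
| First Grade 4 | reduced | previous | no |
| Grade 4 on a reduced dose | next reduced | previous | no |

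Four of the six conflict.

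*Step 2: who is affected.* The footnote speaks of recovery after the scheduled PLD day, so it concerns patients who had not recovered on that day. For them it allows two outcomes: previous dose if counts recover within 14 days, or permanent discontinuation. Neither leaves room for the reduction ordered in the cell. A mid-cycle nadir that has resolved by Day 1 falls outside the footnote and follows the cell alone.

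*Step 3: size of the gap.* Table 4 sets PLD at 40, 30 and 20 mg/m².

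- First reduction: 40 / 30 = 1.33, so the footnote dose is 33% higher.
- Second reduction: 30 / 20 = 1.50, so it is 50% higher.
- Table 4 has no lower level. Section 5.2.6 refers further reductions to the sponsor.

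*Step 4: compare the sibling tables.* Table 9 (hand-foot syndrome) also lowers PLD after Grade 3 or 4 events: "then resume PLD treatment at decreased dose level". Table 10 (stomatitis) does the same. Their double-asterisk footnotes carry only the rule that keeps avelumab aligned with a one-week PLD delay, and no dose rule. In Table 7, a dose rule that suits Grade 2 and first Grade 3 appears to have been attached too widely.

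*Step 5: the single-agent column.* Here the Grade 4 cell offers either a reduced dose or the previous dose with growth factor support, so its conflict with the footnote is only partial. For repeated Grade 3 the cell gives no dose: "If Grade 3 toxicity recurs, follow institutional guidelines". Any rewording must leave both options intact.

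*Step 6: how many patients could still be exposed.* The documents give no count. Assume no delays and no prior anthracycline. At 40 mg/m² every 4 weeks, 11 doses give 11 × 40 = 440 mg/m², and dose 12, at week 44, gives 12 × 40 = 480 mg/m². That passes the 450 mg/m² at which Section 5.2.3.1 calls for special precautions. SAP Section 5.1.1 placed the final analysis at least 12 months after the last randomization, so few patients are likely to remain on PLD. A patient reduced to 30 mg/m² from cycle 2 would have received 40 + 12 × 30 = 400 mg/m² after 13 doses, so some could. Prior anthracycline exposure would bring 450 mg/m² sooner. The 450 mg/m² level is not a fixed stop, so this is only indicative.

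**The case against.** The strongest reply is that a specific instruction normally beats a general one. The cells are specific to grade and recurrence, while the footnote and body text are general recovery-window rules. Letting the footnote win would leave four instructions with little or no work to do. Section 5.2.6 also sends readers to Table 7 alone for combination cytopenia and leaves room for the investigator's medical judgment. Product labeling or institutional guidelines, which are not available here, might settle the dose at a given site.

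This makes the cell the more sensible reading, but it does not make it the stated one. The pointer to Table 7 ranks the table above the body text at most. It cannot rank a cell above the footnote, because the footnote is part of the table. Section 5.2.8 defers first to the protocol's own guidance, which is what conflicts.

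The second reply is that the consequence is slight. That largely stands. Enrollment is complete and the final analysis is done. The conflict needs an Arm B patient still on PLD, with Grade 4 or recurrent Grade 3 cytopenia, a missed Day 1 recovery, and recovery within 14 days. Counts must recover before re-dosing under either reading, and growth factors are permitted (Sections 5.2.8.1 and 5.4.3). The 33% and 50% figures are ratios of dose levels. They say nothing about how often the conflict arises or what harm follows.

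The same footnote raises two other questions: its avelumab delay against cells that keep avelumab on schedule, and its stopping rule against Section 3.1.2, which lets avelumab continue after PLD stops. These are separate from the PLD dose conflict.

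**Conclusion.** The contradiction is real and is in current text. Four of six footnoted instructions in the avelumab-PLD column order a lower PLD dose, while the footnote and body text order the previous one, with no stated precedence. The gap is one dose level, 33% or 50% depending on the step, and it persists unless a later event changes the dose, because Section 5.2.6 forbids re-escalation.

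It should be corrected, because it governs re-dosing of a cytotoxic drug after severe or repeated toxicity and costs almost nothing to repair. It does not bear on the completed primary analysis. That few patients remain exposed is an inference; the documents do not give the number. That the cell reflects the intent is also inferred, from the design of Tables 9 and 10.

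**What to change.** In the Section 5.2.8.1 body text and in the Table 7 double-asterisk footnote, replace the unconditional return to the previous dose with wording such as: on recovery within 14 days, resume PLD as directed in the applicable Table 7 cell. That means:

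- previous dose for Grade 2 and first Grade 3;
- for the combination, reduced or next reduced dose for recurrent Grade 3 and for Grade 4;
- for single-agent PLD, as that column states, including institutional guidelines for recurrent Grade 3.

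Keep the rule to stop if there is no recovery by 14 days. The PLD doses in the cells need no change.

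The cost is one sentence in two places, sent to sites as a clarification letter and carried into the next amendment. No data or analyses change, and no additional patients are needed.
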